[figure not shown]

### *Study Protocol*

The study will be conducted by [name] and his team at the Mayo Clinic. Following an initial home visit to consent the subject and ensure that all study inclusion and exclusion criteria are met, an individual appointment will be scheduled for each subject at the Mayo Clinic. The subjects will meet the health coach, receive training on using the system, and will perform one initial exercise session to ensure safety and cognitive acceptance of the intervention. The training on how to use the system will be conducted by the health coach and will include demonstration, practice, and written materials for subjects to take home. During this initial session at the Mayo Clinic each subject will also provide demographic data and complete a Chronic Respiratory Disease Questionnaire (CRDQ). For the eight week **intervention** period each subject will receive weekly health coaching plus activity monitoring. The health coaching is described below. For the activity monitoring each subject will be asked to wear the ankle and wrist monitor for the entire day, excluding bathing. Each subject will also be asked to wear a fingertip pulse oximeter while completing an exercise routine. Patients will be asked to perform the exercise routine six days a week, including at least a 5 minute walk and walking a total of 15 to 20 minutes during the day for the sole purpose of rehabilitation. The exercise routine will be the same as phase I and each participant will be provided a DVD to follow. Each participant will also have a docking station with a tablet computer. The tablet will prompt the participant daily to answer a brief series of questions on their well-being at the time of taking off the monitors at the end of the day for charging. The subject's daily steps will be available on the wrist monitor and the tablet computer. The tablet will also provide a simplified version of the report that goes to the health coach, including trend and detail data on the subject's daily activity and physiological measures.

During the eight week **control** period no health coaching will be provided or exercise prescription requested. Participants will not receive any information on their activity nor will they be asked to complete the well-being questions. During the last week of the control period all participants will be asked to wear the SenseWear Pro Armband for four days to collect data on their daily steps.

During week 9 all participants (half of whom will be in the intervention period and half in the control period) will be asked to repeat the CRDQ via telephone. At the end of week 17 each participant will be asked to complete the CRDQ via telephone and return all of the equipment.

**Figure 10:** Diagrams showing a few representative low-dynamic exercises.

[figure not shown]
### *Health Coaching*

Each subject will be asked in the first encounter to define a particular place and time in which they can perform rehabilitation. The environment (physical and mental) is a critical piece to adopt new behavior. Each subject will have a weekly coaching call to discuss their rehabilitation and health process with the coach. The calls will be structured using motivational interviewing

[figure not shown]
and will follow the protocol published by [name]. The coach will review with the patient the data from the activity monitoring system (daily steps, physiologic measures – oxygen saturation and heart rate, and duration, frequency, and time of day of the rehabilitation exercise). The coach will also review the daily answers to the well-being questions. Collaboratively, goals for rehabilitation exercise for the following week will be set, based on the information gathered and patients personal preferences (like modifying the exercises or the walking routine, for example, if the exercises initially proposed are not to the liking of the patient). In any case there will be a routine of upper extremity and balance exercises and a walking routine. Each call will last about 12 minutes. All calls will be taped to ensure compliance with the protocol. To complete the intervention, each subject will need to complete phone calls with a health coach at least six out of the eight weeks. At the end of the eight weeks of intervention, a qualitative semi-structured interview will be conducted with each subject by the health coach to gather information on the pros and cons of the process and intervention. This will be in addition to the CRDQ. While the monitoring of the patient will not be real time, any significant physiologic abnormality measured during rehabilitation and transmitted to the server (o2 saturation less than 80% or heart rate > 140 or <40 beats per minute) will prompt a message to the coach to initiate a call to the participant to stop the process and investigate the event. Any time such a call is initiated, the health coach will also contact the subject’s health care provider at the Mayo Clinic COPD practice. [name] will also be alerted anytime such a physiologic abnormality is measured and will ensure that the appropriate response is initiated. Detail of the training of the health coaches has been reported by [name].

**Sample Size**

We calculated the sample size based on our previous published data. A total sample of 104 patients (52 per group) is needed to detect a difference of 0.5 in the Chronic Respiratory Disease Questionnaire (the minimally clinical importance difference) with 80% power. See Figure 11. A sample of 104 patients is necessary to detect a difference of 1000 steps with 80% power. We plan to recruit 115 patients due to an expected attrition of 10% as seen in [name] published research in COPD rehabilitation. See Figure 12.

**Figure 11:** Diagram for power sample size for quality of life outcome

**Figure 12:** Diagram for power sample size for steps outcome

**Analysis Plan**

The primary outcomes of the study are: change in daily steps and change in quality of life between the intervention and control conditions. Change in daily steps will be measured by comparing the mean number of daily steps in weeks 1, 9, and 17 as measured by the activity monitoring system and the SenseWear Pro Armband. Quality of life will be measured by the CRDQ, which consists of 20 items across four dimensions. A change in the score of .5 on the 7 point scale reflects a clinically significant change.

Quantitative analysis: Descriptive and inferential statistics will be used. For daily steps descriptive statistics such as means, standard deviations, medians, ranges, and frequency distributions will be examined and calculated by condition (baseline versus intervention versus control period). The mean number of daily steps of each measurement period (baseline, 9 weeks and 17 weeks in all subjects: intervention, and control) will be compared for differences. A difference of 1000 steps is considered clinically meaningful across all severities of COPD. We will also compare quality of life measured by the CRDQ (baseline versus intervention versus control period). The CRDQ data will be examined for each question, domain, and the entire instrument. We will also analyze daily steps and quality of life trajectories from weeks 1, 9, and 17 using repeated measures models. Regression equations and correlations will be performed to determine the impact of the system/coaching and adherence on outcomes adjusted by the most pertinent variables in COPD (age, dyspnea level, lung function, exacerbations and comorbidities measured by the Charlson comorbidity index).

Multivariate, repeated-measures ANOVA will be used to analyze the main pre- and postintervention effects and interactions both between and within groups. If the overall ANOVA value was significant at the  $p < .05$  level, post hoc independent-samples t tests will be conducted on the subscales of CRDQ

Qualitative analysis: We will conduct semi-structured interviews in the last week of the intervention period with all subjects. These interviews will collect data on the participant's experiences, opinions, perceived benefits and barriers, and impact on self-efficacy for behavior change and actual behavior change. An inductive coding approach will be used to condense these data and to identify themes. These data will be collected to identify potential improvements to study protocol or the system.

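### Daily steps, a primary outcome, have no common counting device: as scheduled, the device changes with condition, so any counting difference between devices enters the treatment effect

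*Combined protocol and SAP*

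**What the plan says.** The Analysis Plan makes change in daily steps one of two primary outcomes and compares the "mean number of daily steps in weeks 1, 9, and 17 as measured by the activity monitoring system and the SenseWear Pro Armband". It later lists the measurement periods as "baseline, 9 weeks and 17 weeks in all subjects: intervention, and control". Neither sentence says which device supplies the value at which time.

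The Study Protocol section sets out device wear by period:

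- **Intervention:** "For the activity monitoring each subject will be asked to wear the ankle and wrist monitor for the entire day, excluding bathing". Participants see their counts: "daily steps will be available on the wrist monitor and the tablet computer".
- **Control:** "Participants will not receive any information on their activity nor will they be asked to complete the well-being questions". The only step measurement scheduled is this: "During the last week of the control period all participants will be asked to wear the SenseWear Pro Armband for four days".
- **End of week 17:** each participant is to "return all of the equipment".

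No section schedules the armband during intervention or the ankle and wrist monitor during control, and none assigns a device to week 1. The supplied text describes no calibration between the devices.

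The Sample Size section states: "A sample of 104 patients is necessary to detect a difference of 1000 steps with 80% power".

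**The concern.** Two step counters of different design, worn at different sites, need not give the same count for the same walking. If one is used under intervention and the other under control, the treatment contrast contains the device difference as well as the treatment effect. A crossover removes stable differences between people and, with balanced sequences, differences between periods. It does not remove a nuisance factor that switches whenever treatment switches. Because no participant is scheduled to wear both devices at once, the data could not be used afterwards to estimate the offset and correct for it.

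Sampling differs as well: all-day monitoring in one condition, four days in the other. If the weekday mix or hours worn differ, that can shift the means too.

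At stake is the interpretation of a primary outcome. A device difference could create an apparent gain, hide a real one, or turn out too small to matter.

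**Working it through.** **Step 1. Device by condition, as scheduled**

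| Time | Ankle and wrist monitor | Armband |
|---|---|---|
| Week 1 baseline | not assigned | not assigned |
| Intervention period | scheduled, all day | not scheduled |
| Control period | not scheduled | four days, last week |

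**Step 2. What the crossover does with an offset.** Let τ be the true effect, b the ankle/wrist count minus the armband count for the same activity, and π the period 1 minus period 2 difference. The expected period 1 minus period 2 difference is:

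- intervention first: π + (τ + b)
- control first: π − (τ + b)

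Half the difference between sequences is τ + b. The period effect cancels and the offset does not. A simulated two-period crossover (104 participants, period effect included, τ = 0) agreed: the mean estimate was 498 steps with b = 500 and 2 steps with b = 0.

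**Step 3. The plan's own figure.** The inputs from Sample Size are 1000 steps, 80% power and 104 participants; 52 per group is stated there for the CRDQ calculation. No SD can be read in the text, so 104 cannot be verified independently. It can only be solved backwards, assuming a two-sided 0.05 t test:

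- 52 versus 52: standardised difference 0.5547; SD = 1000/0.5547 = 1803; SE = 1803 × √(2/52) = 354.
- 104 within-person differences: standardised difference 0.2773; SD of differences = 1000/0.2773 = 3606; SE = 3606/√104 = 354.

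Both readings give an SE of about 354 steps. The normal approximation gives SD 1820 and SE 357.

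**Step 4. Effect of an offset at SE 354.** The rejection probability comes from the noncentral t distribution, with noncentrality b/354 when there is no true effect and (1000 − b)/354 when the offset opposes a true 1000-step effect. The values of b are assumed.

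| Offset b (steps) | False-positive rate | Power for a true 1000 steps, offset opposing |
|---|---|---|
| 0 | 5% | 80% |
| 100 | 5.9% | 71% |
| 300 | 13.4% | 50% |
| 500 | 28.8% | 29% |

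**Step 5. If 1803 is the between-person SD and the analysis is within-person.** SE = 1803 × √(2(1 − ρ))/√104, with the correlation ρ assumed:

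| ρ | SE | False-positive rate, b = 100 | b = 300 | b = 500 |
|---|---|---|---|---|
| 0.3 | 209 | 7.6% | 29.5% | 65.8% |
| 0.5 | 177 | 8.7% | 39.0% | 80.0% |
| 0.7 | 137 | 11.2% | 58.3% | 95.1% |

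Greater precision makes a fixed offset more likely to be declared significant.

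**The case against.** The strongest reply is that the text is ambiguous rather than wrong. The Analysis Plan joins the two devices with *and*, which could mean both are worn at every time point. All equipment comes back only at the end of week 17, so those who have the intervention first may still hold the monitors during control. Withholding activity information in control is compatible with monitoring continuing unseen. This stands as a possible intention, but no section schedules it. If it were intended, each time point would yield two step values and the plan would still not say which is primary.

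Second, the outcome is change. If each sequence used the same device at week 1 as at week 9, an additive offset would cancel from the week 1 to week 9 change compared between groups. That is correct, but it needs a baseline schedule that the plan does not contain, and the offset would remain in the within-person contrast.

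Third, two related criticisms should not be pressed. Visible step counts are part of the intervention, so their effect on walking is not measurement error. A device term in the model would not help, because under this schedule device cannot be distinguished from condition.

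Finally, the offset, SD and correlation are all assumed, and an earlier comparison of the devices may exist outside the supplied text. The figures are therefore scenarios. The gap in the measurement schedule does not depend on them.

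**Conclusion.** The concern holds. That no common device is designated for the primary steps outcome is plain from the text. That device changes with condition follows from the only wear schedule written down. Under that schedule an additive offset passes one-for-one into the within-person comparison, and no later analysis of the same data can separate it from treatment.

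The size and direction of the bias are unknown. At half the plan's own 1000-step clinically meaningful difference, the false-positive rate would be about 29% at the SE implied by the sample size, and roughly 66% to 95% in a within-person analysis with correlation 0.3 to 0.7. At 100 steps it would be 6% to 11%. These figures rest on a two-sided 0.05 test and the back-solved SD. This should be settled before data collection, because it cannot be repaired afterwards.

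**What to change.** Name the SenseWear armband as the single device for the primary steps outcome. Every participant wears it on the same four-day pattern, with the same mix of weekdays and weekend days, at three points:

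1. at baseline, before coaching and step display begin;
2. in the last week of intervention, alongside the ankle and wrist monitor;
3. in the last week of control.

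State in the Analysis Plan that only armband counts enter the primary comparison, and that ankle/wrist counts serve coaching, adherence and secondary description. The shared days in intervention also estimate the device offset. If wearing both devices at every time point is already intended, say so and state whose counts are primary. Ankle/wrist wear in both periods, with counts hidden in control, would also give a common device. The armband is the simpler choice because every participant already wears it in control.

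The cost is small: twelve armband days per participant instead of four (4 + 4 + 4, so eight more), enough armbands to cover the extra wear, and a few sentences of protocol text. The sample size does not change. Duration is also unchanged if week 1 is a baseline week before either period (1 + 8 + 8 = 17). That fits the measurement weeks, but the protocol should state it; if intervention begins in week 1, the baseline days must come before it.

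### The by-condition comparison names no period or order term: the intervention-control contrast loses a little precision, and comparisons with baseline absorb the whole time trend

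*Combined protocol and SAP*

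**What the plan says.** **Design (Study Protocol).** Every patient has an eight-week intervention period and an eight-week control period. Of the latter the protocol says: "During the eight week control period no health coaching will be provided or exercise prescription requested". At week 9 the sample is split, "half of whom will be in the intervention period and half in the control period", and the last assessment is at the end of week 17. One baseline week plus two periods of eight weeks gives 17 weeks, so week 9 closes the first period and week 17 the second. The text does not use the word crossover, but this is a two-period crossover with two orders.

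**Primary outcomes (Analysis Plan).** They are "change in daily steps and change in quality of life between the intervention and control conditions".

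**Comparisons (Analysis Plan).**
- Descriptive statistics for steps are "calculated by condition (baseline versus intervention versus control period".
- For quality of life: "We will also compare quality of life measured by the CRDQ (baseline versus intervention versus control period". This is the sentence that describes a comparison by condition.
- For steps also: "The mean number of daily steps of each measurement period (baseline, 9 weeks and 17 weeks in all subjects: intervention, and control) will be compared".
- Both outcomes also have "trajectories from weeks 1, 9, and 17 using repeated measures models".
- A repeated-measures ANOVA covers "the main pre- and postintervention effects and interactions both between and within groups".

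The regression covariates are age, dyspnea, lung function, exacerbations and comorbidity. Period and order are not among them, and nowhere is either named as a model term.

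**The concern.** A comparison by condition pools the two orders. The intervention value comes from week 9 in one order and from week 17 in the other, and the control value the other way round. Anything that moves all patients between the two weeks (season, disease progression, repeat testing) then enters each patient's intervention-control difference, with opposite sign in the two orders. In the mean it cancels if the orders are equal in size. In the spread it does not cancel.

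Baseline is different, because it is first for everyone and no balancing of orders can remove time from a comparison with it. The CRDQ also changes mode: baseline is completed at the clinic session, weeks 9 and 17 by telephone. An analyst who follows the three-condition comparison literally could report a change from baseline that is only time, repeat testing or mode of completion.

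**Working it through.** **Inputs.** From the Sample Size section: 104 patients, 52 per group, differences of 0.5 CRDQ points and 1000 steps, 80% power. The readable text gives no SD, within-patient correlation or period shift (the two power figures are not shown), so all three are assumptions.

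**The plan's own figure.** Without the SD, 104 cannot be reproduced. Solving back for a two-sided 0.05 parallel comparison: SD = 0.5 / [(1.960 + 0.842) × √(2/52)] = 0.91 points, or 1820 steps. I use 0.90 points. The SD of within-patient differences is SDd = 0.90 × √(2(1 − ρ)): 0.90 at ρ = 0.5 and 0.70 at ρ = 0.7.

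**Intervention versus control.** Let τ be the treatment effect and s the shift from week 9 to week 17. The expected difference is τ − s with intervention first and τ + s with control first. With equal orders the mean is τ, but the variance of the pooled differences is SDd² + s². The ratio of estimated SEs, without versus with a period term, is √(SDd² + s²) / SDd.

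| SDd | s = 0.2 | s = 0.4 |
|---|---|---|
| 0.90 | √0.85 / 0.90 = 1.02 | √0.97 / 0.90 = 1.09 |
| 0.70 | √0.53 / 0.70 = 1.04 | √0.65 / 0.70 = 1.15 |

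At the plan's ratio of 2000 steps per CRDQ point (1000/0.5), the first row also covers shifts of 400 to 800 steps with an SDd of 1800 steps.

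**Direction of the error.** Simulation of 10,000 trials (52 per order, SD 0.91, ρ = 0.5):

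| Shift s | Type I error, no period term | With period term | Power for 0.25 points, no period term | With period term |
|---|---|---|---|---|
| 0.25 | 0.039 | 0.048 | 0.77 | 0.79 |
| 0.5 | 0.025 | 0.050 | 0.71 | 0.80 |

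The unadjusted test is too cautious, not too liberal.

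**Unequal orders.** The bias in absolute size is s × |n₁ − n₂| / N. For an assumed 57 and 47 completers it is 0.2 × 10/104 = 0.02 to 0.4 × 10/104 = 0.04 points. If all 115 recruits completed as 58 and 57, it would be s/115, or 0.002 to 0.003 points.

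**Baseline contrasts.** With drift g per period, week 9 carries g and week 17 carries 2g. Each condition averages (g + 2g)/2 = 1.5g above baseline.
- g = 0.1 gives 0.15 points in both contrasts. With no treatment effect, about 38% of simulated trials reject each one (ρ = 0.5), against about 5% for intervention versus control.
- g = 0.25 gives about 0.37 points and about 98% rejections.
- If the drift were as large as the shifts assumed above (0.2 to 0.4), the contrasts would carry 0.30 to 0.60 points.

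**The other planned models.** If the ANOVA's *groups* are the two orders, week acts as the period term and the group-by-week interaction carries the treatment contrast. The section neither defines the groups nor lists the terms. It does not say which analysis gives the primary contrast. The only follow-up test named is an independent-samples t test on CRDQ subscales, which is not a within-patient estimate.

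**The case against.** The strongest objection is that the plan may already contain what is asked for. It compares weeks 1, 9 and 17, models trajectories over those weeks and plans an ANOVA between and within groups. The Sample Size section speaks of 52 per group, so reading the groups as the two orders is natural. This stands to the extent that a reader might infer from the by-condition wording that the whole analysis ignores period, and the documents do not support that. What they show is that no such term is specified and that no model containing one is tied to the primary contrast.

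Second, the step wording by condition concerns descriptive statistics, which carry no model terms. That is right; the point rests on the CRDQ sentence.

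Third, the cost to the primary contrast is small. At SDd = 0.90 and N = 104 the SE is 0.90/√104 = 0.088. A 9% increase makes it 0.097, and power for 0.5 points goes from about 99.99% to about 99.94%. This also stands: the loss matters only for smaller differences.

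Fourth, the baseline comparisons are not the primary contrast, and the plan does not say they will be read as the treatment effect. True, but the plan lists baseline as one of the three conditions compared and attaches no caution to it.

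**Conclusion.** The point holds as a free improvement in a plan whose primary contrast is basically protected by the balance of orders.

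- *Intervention versus control:* unbiased with equal orders. The estimated SE is 2% to 9% too large at SDd 0.90 and 4% to 15% at 0.70, for shifts of 0.2 to 0.4 points. Unequal completion adds a bias of 0.02 to 0.04 points at most in the split tried, that is, 4% to 8% of the 0.5-point threshold.
- *Comparisons with baseline:* these take in the whole time trend, 1.5 times the drift per period, plus any effect of changing from clinic to telephone.

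A reader might infer that leaving out a period term raises the false-positive rate for intervention versus control, or biases it materially. Neither follows: the unadjusted test is conservative, and the bias needs unequal orders and is small. Inflated false positives arise only if baseline contrasts are tested and read as treatment effects.

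The SDs, correlations, shifts, drift and the 57/47 split are all assumptions. The mechanism does not depend on them; the sizes do.

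**What to change.** In the Analysis Plan:

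1. Name one primary analysis for both CRDQ and daily steps: a mixed model with condition, period (week 9, week 17) and order (intervention first, control first) as fixed effects and patient as a random effect.
2. Take the intervention-control contrast from that model.
3. Define the ANOVA's groups as the two orders and list the terms of the repeated-measures models.
4. Report comparisons with baseline as descriptive only.

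The period term produces the gain in precision. With complete data, order and a single baseline value are between-patient terms that add almost nothing to the within-patient contrast, so baseline as a covariate is optional. If it is used for steps, the plan should first state how the week 1 value is obtained in each order.

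The cost is wording and about one degree of freedom (102 instead of 103 for 104 completers). The period term does not deal with carryover between the two periods or with steps being read on two devices; those are separate matters.

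### Daily steps are analysed from baseline, but the visible procedures schedule no pre-treatment step count, and the intervention-versus-control step contrast is confounded with device

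*Combined protocol and SAP*

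**What the plan says.** **Analysis Plan.** Daily steps is one of two primary outcomes, and baseline or week 1 enters its analysis in four places:

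- The outcome definition: "Change in daily steps will be measured by comparing the mean number of daily steps in weeks 1, 9, and 17". Two devices are named for these three weeks ("as measured by the activity monitoring system and the SenseWear Pro Armband"), without saying which is worn when.
- The descriptive summaries, which "will be examined and calculated by condition (baseline versus intervention versus control period"). Baseline is thus a condition separate from both treatment periods.
- The comparison of means: "daily steps of each measurement period (baseline, 9 weeks and 17 weeks in all subjects: intervention, and control) will be compared for differences".
- The longitudinal model: "We will also analyze daily steps and quality of life trajectories from weeks 1, 9, and 17 using repeated measures models".

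**Study Protocol and Health Coaching.**

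- Initial session: "During this initial session at the Mayo Clinic each subject will also provide demographic data and complete a Chronic Respiratory Disease Questionnaire (CRDQ"). Step counts are not listed.
- Intervention period: the ankle and wrist monitor is worn all day. The participant's "daily steps will be available on the wrist monitor and the tablet computer", and the coach goes over them in the weekly call.
- Control period: "Participants will not receive any information on their activity nor will they be asked to complete the well-being questions". The only step measurement is four days of SenseWear armband wear in the final control week.
- Week 9 and the end of week 17: the CRDQ is repeated by telephone, and the equipment comes back at the end of week 17.

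**The concern.** The analysis text and the procedures do not match. Staff who follow the visible procedures would collect no step count before treatment, yet the plan compares baseline steps with both conditions and starts the step trajectory there. A pre-treatment count that is not taken cannot be recovered later.

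Which device is used for a baseline matters, and the plan does not say. The ankle/wrist system displays steps to the wearer, and that feedback is part of the intervention. A baseline taken with the display on would not be an untreated measurement.

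The same schedule also ties device to condition. Intervention steps come from the ankle/wrist system and control steps from the armband, for everyone. If the two devices count differently, the difference is indistinguishable from a treatment effect on a primary outcome.

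**Working it through.** **Inputs.** Step weeks 1, 9 and 17, and the 1000-step difference (Analysis Plan and Sample Size). Two eight-week periods, and the device used in each (Study Protocol). 104 participants, 52 per group, 115 recruited (Sample Size). These sample sizes serve here only as multipliers. The 104 for steps cannot be reproduced from the text, because no standard deviation is given and the power figure is not shown. Nothing below depends on it.

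**Step 1: which step counts are scheduled.** The period weeks are not stated, so two calendars are checked. A count is taken as scheduled if the week lies in the intervention period (ankle/wrist) or is the last control week (armband).

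| Assumed periods | Sequence | Week 1 | Week 9 | Week 17 |
|---|---|---|---|---|
| Weeks 2–9, 10–17 | Intervention first | none | ankle/wrist | armband |
| Weeks 2–9, 10–17 | Control first | none | armband | ankle/wrist |
| Weeks 1–8, 9–16 | Intervention first | ankle/wrist, on treatment | none | none |
| Weeks 1–8, 9–16 | Control first | none | ankle/wrist, first treatment week | none |

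- The first calendar fits best: 1 + 8 + 8 = 17, with equipment returned at the end of week 17. It fills 4 of 6 cells, or 4 × 52 = 208 of 6 × 52 = 312 values. Both empty cells are week 1 (0 of 104 values).
- The second fills 2 of 6 cells, or 104 of 312 values, both from a first week on treatment. Week 17 then falls after both periods.
- On either calendar, pre-treatment step counts are scheduled in 0 of 2 sequences.

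**Step 2: what this leaves.** Three conditions give three pairwise contrasts. Two need baseline and have no scheduled pre-treatment data. On the first calendar the trajectory reduces to weeks 9 and 17.

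**Step 3: device in the remaining contrast.** Let τ be the true intervention-minus-control difference, d the ankle/wrist-minus-armband offset, and p the change from period 1 to period 2. The observed intervention-minus-control difference is:

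- intervention first: τ + d − p
- control first: τ + d + p
- average: τ + d

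The crossover cancels p. It does not cancel d, which has the same sign in both sequences. The documents give no value for d. Over an assumed range, as a share of the 1000-step difference:

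| Assumed offset d, steps/day (either sign) | d / 1000 |
|---|---|
| 100 | 10% |
| 250 | 25% |
| 500 | 50% |

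**Step 4: contrasts available on one device.** As scheduled, 0 of 3. With a baseline armband wear added, 1 of 3 (baseline versus control). With armband wear in the last intervention week as well, 3 of 3.

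**The case against.** The strongest reply is that the Analysis Plan itself names week 1 and two devices. With a 17-week calendar that leaves room for a set-up week, a baseline measurement may well have been intended, with its wear instructions simply not repeated in the Study Protocol. Several figures are also missing from the text available here, and one of them may hold the schedule. The calendars above are inferred, so the cell counts depend on that inference.

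Much of this stands. A reader might infer that no baseline step count was planned, or that the step outcome cannot be analysed. The documents support neither. What they show is that the visible procedures state no device, duration or timing for a pre-treatment count, and that holds on both calendars.

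A reader might also infer that any baseline must leave one baseline contrast mixing devices. That fails if both devices were worn in week 1, which the text does not exclude.

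Finally, the primary comparison is between intervention and control, and each participant supplies both. It can therefore be estimated without a baseline. This limits the harm from the missing baseline, but it does not answer the device problem. That problem is separate, would remain even with a perfect baseline, and falls on exactly this comparison.

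**Conclusion.** The point holds and should be fixed; it is not fatal to the trial. It has two parts.

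1. As the procedures read, both baseline step contrasts and the first trajectory point have no scheduled pre-treatment data, in either sequence. This rests on the visible text and lapses if a missing figure schedules a baseline wear.
2. The intervention-versus-control step contrast is confounded with device in every participant, and a between-device offset passes into it in full. The size and direction of any offset are unknown from the documents, so no actual bias is claimed.

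The point does not reach the CRDQ, whose baseline is collected at the initial session. Nor does it show that the sample size is wrong.

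**What to change.** - **Baseline wear.** Have every participant wear the SenseWear armband for four days, without step feedback, between the home consent visit and the initial Mayo session. The count then precedes training and the first exercise session.
- **End-of-intervention wear.** Have the armband worn for four days in the last intervention week as well, matching the existing control-week wear.
- **Analysis text.** Use armband counts for all step comparisons, and state the weeks of each period explicitly.

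Cost: 115 × 4 = 460 armband person-days for each added wear, so 2 × 460 = 920 for both. The baseline wear also needs at least four days between the home visit and the Mayo session; the Study Protocol gives no interval.

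**If no baseline wear is added,** remove baseline and week 1 from every step analysis and define the primary step outcome as within-patient end-of-intervention versus end-of-control steps. That costs only wording but gives up any pre-treatment reference. It does not remove the device confounding, for which the end-of-intervention armband wear is still needed.

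**If a figure already schedules a baseline wear,** state its device and timing in both the Study Protocol and the Analysis Plan.
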